2.4.3 Bempegaldesleukin and Nivolumab Benefit and Risk Assessment

Bempegaldesleukin has been generally well-tolerated in the clinical studies to date, both as monotherapy as well as in combination with nivolumab, with promising evidence of clinical efficacy and a potentially favorable benefit-risk profile. Bempegaldesleukin has been safely administered in an outpatient setting supported by appropriate clinical monitoring.

Hypotension has been identified as a clinically significant adverse effect of bempegaldesleukin and can be effectively mitigated by prophylaxis and hydration guidelines. Other risks associated with bempegaldesleukin include IL-2 mediated AEs (e.g., flu-like symptoms, rash, pruritus, fatigue, hepatic transaminase elevations, and serum creatinine elevation), infusion-related reactions, thyroid dysfunction, eosinophilia, and arthralgia; these AEs are generally mild or moderate in severity, and can be monitored and managed in clinical setting. Cases of thyroid dysfunction (hypothyroidism, hyperthyroidism, thyroiditis), dermatitis, pneumonitis, hepatitis, myocarditis, myositis/myasthenia gravis, and vitiligo/hypopigmentation consistent with immune-mediated mechanism have been observed in patients receiving bempegaldesleukin plus nivolumab, and some of these cases shared clinical characteristics consistent with immune-mediated AEs associated with checkpoint inhibitors.

The continued development of bempegaldesleukin in combination with nivolumab for the treatment of various cancers is warranted based on a positive benefit-risk profile. In addition, the

early efficacy data along with the correlative biomarker showing conversion of PD-L1 negative patients to PD-L1 positive patients suggests that the addition of bempegaldesleukin to a checkpoint inhibitor (nivolumab) may change the tumor microenvironment in PD-L1 negative patients such that the combination may contribute to antitumor activity with an acceptable safety profile.

In conclusion, the currently available safety data demonstrates that bempegaldesleukin and nivolumab is a well-tolerated immuno-oncology combination therapy. Given the encouraging clinical activity and manageable and generally non-overlapping toxicity profile, the potential for direct benefit in patients warrants continued evaluation of the combination bempegaldesleukin and nivolumab in the clinical setting and supports further development of combination of bempegaldesleukin and nivolumab regimens in patients with cancer.

2.4.4 Independent Data Monitoring Committee

In addition to routine safety monitoring and pharmacovigilance activities, an Independent Data Monitoring Committee (IDMC) will be formed to independently monitor and assess accumulating safety data and emerging benefit-risk balance at regular intervals throughout the study, at the interim analyses, and on an ad hoc basis as detailed in the IDMC charter (see Section 9.10).

3.0 STUDY OBJECTIVES

3.1 Primary Objective

The primary objective is to compare the efficacy, as measured by RFS by BICR, of bempegaldesleukin plus nivolumab versus nivolumab in patients with completely resected Stage IIIA (LN metastasis > 1 mm), Stage IIIB/C/D, or Stage IV (AJCC 8th edition) cutaneous melanoma with no evidence of disease (NED) who are at high risk for recurrence.

3.2 Secondary Objectives

The secondary objectives are:

- To compare the OS of bempegaldesleukin plus nivolumab versus nivolumab in patients with completely resected Stage IIIA (LN metastasis > 1 mm), Stage IIIB/C/D, or Stage IV NED melanoma
- To evaluate DMFS by BICR and by Investigator in patients who have Stage IIIA (LN metastasis > 1 mm) or IIIB/C/D melanoma at study entry
- To evaluate time to disease progression after the next line of treatment for study patients following discontinuation of bempegaldesleukin plus nivolumab versus nivolumab
- To assess the overall safety and tolerability of bempegaldesleukin plus nivolumab versus nivolumab in study patients
- To describe changes in patient-reported outcomes (PROs) as assessed by the global health/quality of life (GH/QoL) and physical functioning subscales of the 30-item European Organisation for Research and Treatment of Cancer Core Quality of Life Questionnaire (EORTC QLQ-C30)
- To evaluate the association between PD-L1 expression status and RFS by BICR
- To assess the efficacy, as measured by RFS by Investigator, of bempegaldesleukin plus nivolumab versus nivolumab in patients with completely resected Stage IIIA (LN metastasis > 1 mm), Stage IIIB/C/D, or Stage IV NED melanoma

3.3 [REDACTED]

[REDACTED]

[REDACTED]

[REDACTED]

[REDACTED]

- [REDACTED]
- [REDACTED]
- [REDACTED]
[REDACTED]
- [REDACTED]
[REDACTED]
- [REDACTED]
[REDACTED]

4.0 SELECTION OF STUDY POPULATION

4.1 Inclusion Criteria

Each patient will be entered into this study only if he/she meets all of the following criteria:

1. Provide written, informed consent to participate in the study and follow the study procedures. The Investigator takes responsibility for ensuring that all vulnerable patients are protected and participate voluntarily in an environment free from coercion or undue influence. (See Section 5.2 for details about obtaining informed consent for adolescent patients.)
2. Male or female patients ≥ 12 years of age at the time of signing the informed consent form (ICF), except where local regulations, countries, and/or institutional policies do not allow for patients < 18 years of age (adolescents) to participate. In regions where adolescents are not allowed to participate in the study due to age restrictions, enrolled patients must be ≥ 18 years of age.
3. Patients must have an Eastern Cooperative Oncology Group (ECOG) performance status of 0 or 1 (≥ 17 years of age)/Lansky Performance Score $\geq 80\%$ (12 to 16 years of age, inclusive) (for details, see [Appendix 3](#)).
4. Histologically confirmed Stage IIIA (LN metastasis > 1 mm [i.e., at least one LN metastasis measuring > 1 mm at greatest diameter]), IIIB/C/D, or IV (M1a/b/c/d) cutaneous melanoma by AJCC (8th edition) at study entry.
 - Patient must be completely surgically resected within 12 weeks prior to randomization.
 - Patients with in-transit or microsatellite disease will be allowed if disease has been completely surgically resected.
 - Patients must have been surgically rendered free of disease with negative surgical margins documented, as applicable.

Please refer to Section 5.2 for details of minimum documentation requirements and [Appendix 2](#) for AJCC 8th edition definitions of TNM and staging.

5. Prior treated central nervous system (CNS) metastases must have magnetic resonance imaging (MRI) evidence of no recurrence for at least 4 weeks after treatment, subjects must be off immunosuppressive doses of systemic steroids (> 10 mg/day or equivalent) for at least 14 days prior to study drug administration and must have returned to neurologic baseline post-operatively. (The 4-week period of stability is measured after the completion of the neurologic interventions [i.e., surgery and/or radiation]). (Note: Leptomeningeal disease is excluded.)
6. In addition to neurosurgery to treat CNS metastases, adjuvant radiation after the resection of CNS metastasis is allowed. Immunosuppressive doses of systemic steroids (doses > 10 mg/day prednisone or equivalent) must be discontinued at least 14 days before study drug administration.

7. Tumor tissue available from biopsy or resected disease must be provided to central laboratory for biomarker and PD-L1 status analysis. Must have PD-L1 expression classification ($\geq 1\%$, $< 1\%$, indeterminate, or not evaluable) prior to randomization.
8. Disease-free status documented by a complete physical examination and imaging studies within 28 days prior to randomization (see [Table 1](#) for details of required assessments).
9. Demonstrated adequate organ function, as defined below:
 - a. White blood cells $\geq 2000/\mu\text{L}$
 - b. Absolute neutrophil count $\geq 1500/\mu\text{L}$ ($1.5 \times 10^9/\text{L}$)
 - c. Hemoglobin $\geq 9.0 \text{ g/dL}$ (90 g/L)
 - d. Platelet count $\geq 100 \times 10^9/\text{L}$
 - e. Total bilirubin $\leq 1.5 \times$ upper limit of normal (ULN) (except patients with Gilbert Syndrome, who must have total bilirubin $< 3.0 \text{ mg/dL}$)
 - f. Alanine aminotransferase (ALT) $\leq 3 \times$ ULN
 - g. Aspartate aminotransferase (AST) $\leq 3 \times$ ULN
 - h. Serum creatinine $\leq 1.5 \times$ ULN ($133 \mu\text{mol/L}$) OR calculated creatinine clearance $\geq 50 \text{ mL/min}$ (using Cockcroft-Gault formula and actual body weight)
10. A documented left ventricular ejection fraction (LVEF) $> 45\%$ using standard echocardiogram or multigated acquisition (MUGA) scan test.
11. Reproductive Status
 - a. Women of childbearing potential (WOCBP) must have a negative serum or urine pregnancy test (minimum sensitivity 25 IU/L or equivalent units of human chorionic gonadotropin [HCG]) within 14 days prior to the start of study treatment.
 - b. Women must not be breastfeeding
 - c. WOCBP must agree to follow instructions for methods of contraception for the duration of treatment with study treatment and for 5 months after bempegaldesleukin and/or nivolumab treatment completion. Women should use effective methods of contraception as indicated in [Appendix 4](#). WOCBP who are continuously not heterosexually active are exempt from contraceptive requirements, and still must undergo pregnancy testing as described in this protocol.
 - d. Males who are sexually active with WOCBP must agree to follow instructions for method(s) of contraception ([Appendix 4](#)) for the duration of treatment with bempegaldesleukin and 3 months after bempegaldesleukin treatment completion. In addition, male patients must be willing to refrain from sperm donation during this time.
12. Patients must be able and willing to comply with the study visit schedule and study procedures.

4.2 Exclusion Criteria

A patient will be excluded from this study if he/she meets any of the following criteria:

1. Use of an investigational agent or an investigational device within 28 days before randomization.
2. Female patients who are pregnant or lactating, who plan to get pregnant, or who have a positive serum or urine pregnancy test.
3. History of ocular/uveal melanoma or mucosal melanoma.
4. Active, known or suspected autoimmune disease. Patients with Type I diabetes mellitus, hypothyroidism only requiring hormone replacement, skin disorders (such as vitiligo, psoriasis, or alopecia) not requiring systemic treatment, or conditions not expected to recur in the absence of an external trigger are permitted to enroll.
5. Conditions requiring systemic treatment with either corticosteroids (> 10 mg daily prednisone equivalent) or other immunosuppressive medications within 30 days of randomization. Inhaled or topical steroids, and adrenal replacement steroid doses > 10 mg daily prednisone equivalent, are permitted in the absence of active autoimmune disease.
6. Prior therapy for melanoma. Exceptions include surgery for the melanoma lesion(s) and/or adjuvant radiation therapy for CNS lesions at least 28 days prior to randomization. Patients must have recovered from all Grade ≥ 2 radiation-related toxicities.
7. Prior therapy with interferon, talimogene laherparepvec (Imlygic[®]), IL-2 directed therapy, anti-PD-1, anti-PD-L1, anti-PD-L2, anti-CD137, or anti-CTLA-4 antibody (including ipilimumab or any other antibody or drug specifically targeting T cell co-stimulation or checkpoint pathways).
8. History of leptomenigeal disease.
9. History of hypersensitivity or allergy to study drug components (for nivolumab, bempegaldesleukin, or any of their excipients).
10. History of severe hypersensitivity reaction to any monoclonal antibody.
11. Prior malignancy active within the previous 3 years **except for locally potentially curable cancers that have been apparently cured**, such as basal or squamous cell skin cancer, superficial bladder cancer, or carcinoma in situ of the prostate, cervix, or breast. Consult with the Medical Monitor about prior melanoma or other potential exceptions.
12. History of allogeneic stem cell transplant; history of solid organ or tissue transplant that requires systemic use of immune suppressive agents.
13. Prior surgery that required general anesthesia within 28 days before the first dose of study treatment; surgery requiring local/epidural anesthesia within 72 hours before first dose.
14. Active infection requiring systemic therapy within 14 days prior to randomization.

15. History of idiopathic pulmonary fibrosis (including pneumonitis), drug-induced pneumonitis, organizing pneumonia (i.e., bronchiolitis obliterans, cryptogenic organizing pneumonia), or evidence of active pneumonitis on Screening chest computed tomography (CT) scan.
16. Any positive test result for hepatitis B virus or hepatitis C virus indicating presence of virus (e.g., hepatitis B surface antigen [HBsAg, Australia antigen] positive, or hepatitis C antibody [anti-HCV] positive [except if HCV-RNA negative]).
17. Any positive test result for immunodeficiency or active human immunodeficiency virus (HIV-1/2 antibodies).
18. Prolonged Fridericia's corrected QT interval (QTcF) > 450 ms for men and > 470 ms for women at Screening.
19. Unstable or deteriorating cardiovascular disease within the previous 12 months prior to Screening including, but not limited to, the following:
 - a. Unstable angina or myocardial infarction
 - b. Congestive heart failure (New York Heart Association Class III or IV)
 - c. Uncontrolled clinically significant arrhythmias
20. Transient ischemic attack (TIA) or CVA within 12 months prior to Screening
21. Need for > 2 antihypertensive medications for management of hypertension (including diuretics). Patients with hypertension must be on a stable antihypertensive regimen for the 14 days prior to randomization.

Note: An antihypertensive medication that contains 2 drugs under one formulation is counted as 2 antihypertensive medications (e.g., angiotensin-converting-enzyme [ACE] inhibitor plus diuretic, calcium channel blocker plus ACE inhibitor).
22. History of pulmonary embolism, deep vein thrombosis, or prior clinically significant venous or non-CVA/TIA arterial thromboembolic event (e.g., internal jugular vein thrombosis) within 3 months prior to randomization.

Note: Patients with a history of a venous or arterial thromboembolic event must be asymptomatic for at least 2 weeks prior to randomization and must be receiving a stable regimen of therapeutic anticoagulation (preferably low molecular weight heparin [LMWH] or direct oral anticoagulation [DOAC]; see Section 5.13.2.3 for further guidance).

Note: Unless there is a new medical contraindication observed after Cycle 1 Day 1, a patient with a history of venous or arterial thromboembolic event must be maintained on therapeutic anticoagulation throughout participation on the treatment phase of the study.
23. Patients with inadequately treated adrenal insufficiency.
24. Patients who have received a live/attenuated vaccine within 30 days of randomization.

25. Known current drug or alcohol abuse.
26. Receiving any medication prohibited in combination with study treatments as described in the respective product labels, unless medication was stopped within 7 days prior to randomization.
27. Any condition including medical, emotional, psychiatric, or logistical that, in the opinion of the Investigator, would preclude the patient from adhering to the protocol or would increase the risk associated with study participation or study drug administration or interfere with the interpretation of safety results (e.g., a condition associated with diarrhea or acute diverticulitis).

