5.10.3 Criteria to Resume Bempegaldesleukin and/or Nivolumab

Patients may resume treatment when the treatment-related AE(s) resolve(s) to Grade ≤ 1 or baseline, with the following exceptions:

- Patients may resume treatment in the presence of Grade 2 fatigue.
- Patients who have not experienced a Grade 3 treatment-related skin AE may resume treatment in the presence of Grade 2 skin toxicity.
- Patients with baseline Grade 2 AST/ALT and/or total bilirubin abnormalities may resume dosing when laboratory values return to baseline and management with corticosteroids, if needed, is complete.
- Treatment-related pulmonary toxicity, diarrhea, or colitis must have resolved to baseline before treatment is resumed. Patients with persistent Grade 1 pneumonitis after completion of a steroid taper over at least 1 month may be eligible to resume study treatment if discussed and approved by Medical Monitor.
- Patients with treatment-related endocrinopathies adequately controlled with only physiologic hormone replacement may resume treatment after consultation with the Medical Monitor (or designee). Grade ≥ 3 adrenal insufficiency and/or Grade 4 hypophysitis require discontinuation regardless of control with hormone replacement (see Section 5.12.1 for permanent treatment discontinuation criteria). Hospitalization for diagnostic workup of adrenal insufficiency without severe symptoms should not require discontinuation.

- For patients who must delay study treatment due to Grade ≥ 2 creatinine increase due to a non-inflammatory cause (Section 5.10.1), delay retreatment with study drug for approximately 3 to 5 days. After the dosing delay, the patient may resume study drug when serum creatinine has returned to Grade ≤ 1 , as assessed within 24 hours prior to redosing (or as soon as locally feasible), except where permanent discontinuation of study drug is required (Section 5.12.1).

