5.13.2.2 Steroids

Patients are permitted the use of topical, ocular, intra-articular, intranasal, and inhalational corticosteroids (with minimal systemic absorption). Patients with pre-existing adrenal impairment requiring corticosteroid supplementation may be at increased risk for hypotensive episodes during treatment with bempegaldesleukin. For these patients, their existing corticosteroid dose may be increased to adrenal replacement steroid doses > 10 mg of daily prednisone or equivalents for the first 4 days after administration of bempegaldesleukin based on an assessment of the degree of adrenal impairment and the extent of existing corticosteroid supplementation. A brief (less than 3 weeks) course of corticosteroids for prophylaxis (e.g., contrast dye allergy) or for treatment of non-autoimmune conditions (e.g., delayed-type hypersensitivity reaction caused by a contact allergen) is permitted. Use of corticosteroids for the management of immune-mediated AEs as outlined in the nivolumab Investigator's Brochure is permitted. Short-term use of systemic corticosteroids or immunosuppressive medication is permitted if administered for AE treatment. Daily dosage of prednisone or equivalents must be ≤ 10 mg for study treatment to resume.

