5.13.3 Prohibited and/or Restricted Concomitant Medications

5.13.3.1 Prohibited Medications

- Immunosuppressive agents
- Immunosuppressive doses of systemic corticosteroids (except as stated in Section 5.13.2) defined as a daily dose of greater than 10 mg prednisone equivalents
- Any concurrent systemic antineoplastic therapy for the treatment of melanoma or a new malignancy (except as noted). Patients who develop a new non-melanoma fully resectable malignancy (examples include but are not limited to: in situ bladder cancer, in situ gastric cancer, or in situ colon cancers; in situ cervical cancers/dysplasia; or breast carcinoma in situ; or prostate carcinoma) during the study may continue receiving study drugs if the only therapy required is hormonal therapy, surgery and/or radiation (and the surgery or radiation site does not overlap with a previous primary melanoma or melanoma metastasis location). Consultation with the Medical Monitor is required once a new malignancy is detected.
- Any live / attenuated vaccine (e.g., varicella, zoster, yellow fever, rotavirus, oral polio, and measles, mumps, rubella or Flumist® Quadrivalent) during treatment and until 100 days post last dose of nivolumab. Note: All vaccines available as of the date of this document against severe acute respiratory syndrome coronavirus 2 (SARS-CoV-2; COVID-19) are allowed on treatment. For any questions about COVID vaccines, please contact the Medical Monitor.

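### Exclusion 5 admits patients on pre-existing adrenal replacement above 10 mg/day prednisone equivalent, but Section 5.13.3.1 prohibits that dose on study and 5.13.2.2 excepts it only for 4 days after bempegaldesleukin (minor inconsistency)

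*Protocol*

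**What the plan says.** Exclusion 5 (Protocol 4.2, repeated in the synopsis) bars conditions that need more than 10 mg/day prednisone equivalent within 30 days of randomization, then makes an allowance: "adrenal replacement steroid doses > 10 mg daily prednisone equivalent, are permitted in the absence of active autoimmune disease". Exclusion 23 bars "Patients with inadequately treated adrenal insufficiency".

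On study, Section 5.13.3.1 lists as prohibited: "Immunosuppressive doses of systemic corticosteroids (except as stated in Section 5.13.2) defined as a daily dose of greater than 10 mg prednisone equivalents". Section 5.13.2.2 is therefore where any exception has to be found. For patients with pre-existing adrenal impairment it says that the "existing corticosteroid dose may be increased to adrenal replacement steroid doses > 10 mg of daily prednisone or equivalents for the first 4 days" after bempegaldesleukin. Its other permissions are:

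- routes with minimal systemic absorption;
- "A brief (less than 3 weeks) course of corticosteroids for prophylaxis (e.g., contrast dye allergy) or for treatment of non-autoimmune conditions";
- corticosteroids to manage immune-mediated adverse events;
- "Short-term use of systemic corticosteroids or immunosuppressive medication is permitted if administered for AE treatment".

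Its closing sentence requires a daily dose no higher than 10 mg prednisone equivalent before study treatment restarts.

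**The concern.** Eligibility is confirmed before randomization, so the Exclusion 5 allowance applies whichever arm the patient is assigned to. The concomitant-medication rule does not carry the allowance forward. Exclusion 23 adds to the tension, because it expects adrenal insufficiency to be adequately treated at entry. A patient whose adequate dose is above 10 mg/day passes both exclusions and is then on a dose that the on-study rule forbids.

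Obeying the prohibition literally would mean lowering a replacement dose the patient needs. Section 5.13.2.2 itself notes that such patients may be more prone to hypotension on bempegaldesleukin. The more likely result is a query, or a deviation that Section 11.1 requires to be documented and reported, for a patient enrolled exactly as the criteria allow.

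**Working it through.** The plan gives no figure to reproduce, and the point depends on no sample size, power or event count. The check is a comparison of text.

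1. **Is replacement above 10 mg/day eligible?** Yes, under Exclusion 5, if there is no active autoimmune disease. The allowance is not limited by arm.

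2. **Does the on-study prohibition reach it?** Yes, as written. Section 5.13.3.1 defines an immunosuppressive dose by amount alone, not by indication. Inclusion 6 uses the same cut-off for patients with resected CNS metastases: "Immunosuppressive doses of systemic steroids (doses > 10 mg/day prednisone or equivalent) must be discontinued at least 14 days before study drug administration". The word immunosuppressive therefore does not by itself exempt replacement use. Exclusion 5 needed an express carve-out for adrenal replacement; 5.13.3.1 has none of its own.

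3. **Does an exception in 5.13.2 cover continuing pre-existing replacement?** The 4-day increase is tied to bempegaldesleukin. The brief course must last less than 3 weeks. The adverse-event permissions concern events treated on study. The local-route permission does not concern systemic replacement. None fits.

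4. **Does a rule elsewhere help?** Section 5.10.3 says "Patients with treatment-related endocrinopathies adequately controlled with only physiologic hormone replacement may resume treatment after consultation with the Medical Monitor". That concerns endocrinopathies caused by treatment, and it lies outside 5.13.2, the only place to which 5.13.3.1 points for exceptions.

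5. **Which doses are affected?** Appendix 5 equates 10 mg prednisone with 40 mg hydrocortisone, so only replacement above 40 mg/day hydrocortisone equivalent is caught.

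The literal position of a patient on stable pre-existing replacement is then:

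| Situation | Dose at or below 10 mg/day | Dose above 10 mg/day |
|---|---|---|
| Arm A, first 4 days after bempegaldesleukin | allowed | excepted, as an increase |
| Arm A, other days, or bempegaldesleukin stopped and nivolumab continued | allowed | prohibited |
| Arm B, any day | allowed | prohibited |
| Resuming after a dose delay, either arm | allowed | barred, if the closing sentence of 5.13.2.2 is read as general |

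The last row is less certain than the others. That sentence directly follows the one on steroids for adverse events and may have been meant only for them.

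**The case against.** The strongest reply is that the two rules govern different periods. Exclusion 5 is an entry criterion with a 30-day window, not a promise about treatment. Section 5.13.2.2 speaks of increasing an existing dose to above 10 mg, which suggests maintenance at or below 10 mg with a short rise around each bempegaldesleukin dose. That reading is available, but it does not remove the problem: a patient who needs more than 10 mg/day is still eligible, and still has no permitted way to stay on that dose.

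A second reply concerns size, and it stands. Section 5.12.1, in its list of Grade 4 exceptions, describes physiologic hormone replacement as corticosteroids at or below 10 mg prednisone equivalent per day. On that description ordinary replacement never meets the prohibition, and the affected group is close to empty.

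A third reply is that the intent is plain. Exclusion 23, the advice in 5.11.2 on co-management with an endocrinologist, and 5.13.2.2 all presuppose that patients with adrenal insufficiency stay on replacement. Continuation was probably intended. That limits the consequence but leaves the text wrong.

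A reader might also infer two stronger claims that the documents do not support:

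- **That Arm B has no route to steroids for any adrenal problem.** Section 5.13.2.2 permits corticosteroids for immune-mediated adverse events in either arm, so adrenal insufficiency arising on nivolumab has a route. The gap is confined to pre-existing replacement.
- **That Arm B was wrongly denied the 4-day increase.** The increase answers a hypotension risk attributed to bempegaldesleukin, which Arm B does not receive. Its absence there is reasonable.

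**Conclusion.** The inconsistency is real and the text is wrong as written, at low severity. It holds for pre-existing adrenal replacement above 10 mg/day prednisone equivalent: in Arm B throughout treatment, and in Arm A outside the 4 days after each bempegaldesleukin dose. It rests on reading 5.13.3.1 by its own dose-only definition.

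The documents give no count of such patients; few if any are likely. It would be wrong to infer a material safety problem or any threat to the trial's conclusions. There is no effect on RFS, power or alpha. The SAP (Sections 2.0 and 3.0) also records that the study was discontinued and that concomitant-medication and important-deviation analyses will not be performed, so a deviation of this kind would enter no planned analysis. That does not mend the wording, which matters for patient care and for any reuse of the protocol text.

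**What to change.** Make three edits, all in Section 5.13.2.2, which 5.13.3.1 already cites as the source of its exceptions:

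1. Add: *Stable pre-existing adrenal replacement permitted under Exclusion 5, including doses > 10 mg/day prednisone equivalent, may continue throughout study treatment in both arms.*
2. Reword the 4-day increase as an additional Arm A allowance above the patient's existing dose.
3. Exempt stable adrenal replacement from the closing sentence that sets a 10 mg ceiling for resuming study treatment. Without this, the patient whom the first edit protects could still be barred from restarting after a dose delay.

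The cost is one added sentence and two wording changes, with no added procedures, visits or patients.

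### Exclusion 26 sets no minimum drug-free interval for label-prohibited medication, because its 7 days is written as a maximum

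*Protocol*

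**What the plan says.** In Protocol Section 4.2, meeting any one listed criterion excludes the patient. Exclusion 26 lists current receipt of a medication prohibited in combination with study treatment under the respective product labels, with one exception: "unless medication was stopped within 7 days prior to randomization". Section 5.3 asks for the first dose within 5 calendar days of randomization and sets no minimum delay.

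Other criteria place their time limits differently:

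- Exclusion 1: "Use of an investigational agent or an investigational device within 28 days before randomization".
- Exclusion 5: "other immunosuppressive medications within 30 days of randomization".
- Exclusion 13: "Prior surgery that required general anesthesia within 28 days before the first dose of study treatment".
- Exclusion 14: "Active infection requiring systemic therapy within 14 days prior to randomization".
- Exclusion 24: "Patients who have received a live/attenuated vaccine within 30 days of randomization".
- Exclusion 6, also an exception: "adjuvant radiation therapy for CNS lesions at least 28 days prior to randomization".
- Section 4.1, Inclusion 5, on immunosuppressive steroid doses: off them "for at least 14 days prior to study drug administration". Inclusion 6 has a matching 14-day minimum.

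**The concern.** In an exclusion criterion, 'within N days' works as a washout only when it describes the exposure that excludes the patient. Exclusion 1 does this: use in the last 28 days excludes, so at least 28 days must have passed. In Exclusion 26 the phrase sits in the exception instead. There it describes who is let in, so 7 days becomes the longest time since stopping and no shortest time is given.

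A site following the text literally could randomize a patient one day after the last use of a prohibited drug and dose the same day. What is at stake is a safety precaution at entry and its uniform use across sites. It is not the treatment comparison.

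**Working it through.** No figure in the plan depends on this clause, so there is nothing to reproduce. The check is a reading of the wording followed by a day count.

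**Wording in Section 4.2.** Used as a time window, 'within' appears 11 times in 10 criteria: Nos. 1, 5, 11, 13 (twice), 14, 19, 20, 22, 24 and 26.

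- In nine of these criteria (10 uses) it describes the exposure or event that excludes the patient. In Nos. 1, 5, 13, 14 and 24 the effect is a washout or recovery period.
- In one criterion (No. 26, 1 use) it stands in the exception.
- The only other exception in Section 4.2 with a time limit, in No. 6, uses 'at least'.

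**Wording in Section 4.1.** Where a qualifying clause uses 'within', it means a maximum: resection no more than 12 weeks before randomization (Inclusion 4), imaging no more than 28 days before (Inclusion 8), and a pregnancy test no more than 14 days before treatment (Inclusion 11a). Where a minimum is meant, Inclusions 5 and 6 write 'at least'. So 'within 7 days' cannot be read as this protocol's usual way of writing 'at least 7 days'.

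**Other sections.** Section 5.13.2.1 manages interactions on Days 3 to 7 after a bempegaldesleukin dose. Section 5.13.3.1 lists drugs prohibited during the study. Neither sets a pre-dose interval for label-prohibited drugs as a group.

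**Day count.** Take randomization as day 0, let *s* be the day of stopping and *d* the day of first dose, with *d* from 0 to 5 (Section 5.3). Interval from stop to first dose = *d* − *s*.

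- Current text, stop on day -1: 0 − (−1) = 1 day up to 5 − (−1) = 6 days.
- With 'at least 7 days', latest allowed stop on day -7: 0 − (−7) = 7 days up to 5 − (−7) = 12 days.

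The shortest permitted interval thus rises from 1 day to 7 days.

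**The case against.** The strongest reply is that the gap may contain no drugs. Exclusion 26 refers to product labels that are not in the documents. The protocol cites labels for nivolumab (Sections 2.3.2 and 2.4.2), but for bempegaldesleukin it relies on an Investigator's Brochure (Section 2.4.1). It names no affected drug. The classes it does prohibit in Section 5.13.3.1 (immunosuppressants, higher-dose steroids, antineoplastic therapy and live vaccines) are addressed at entry by Inclusions 5 and 6 and Exclusions 1, 5, 6, 7, 11 and 24. Exclusion 27 lets the investigator refuse a patient at increased risk. All of this stands, and it limits the size of the point. It does not supply the missing minimum.

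The SAP also records that the programme was ended in April 2022, with about 774 patients enrolled. A correction now matters only for the protocol text and any reuse of it. The rule still says what it says.

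Four stronger readings are tempting, and the documents do not support them:

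- *The rule is inverted and excludes patients who stopped more than 7 days earlier.* Such patients are no longer receiving the drug, so the criterion does not reach them.
- *The 7 days can only be a washout.* 'Receiving' could describe status at Screening, where medication use is reviewed within 14 days before randomization (Table 1). The exception would then cover a drug stopped between Screening and randomization. Washout is the likelier intent, but it remains an inference.
- *A stop on the day of randomization qualifies, giving an interval of 0 days.* Whether a same-day stop counts as prior to randomization is arguable, so the day -1 figures are the ones to use.
- *Patients were harmed or the comparison was biased.* Nothing in the documents shows harm, and the rule acts before randomization in both arms.

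**Conclusion.** The point holds as a minor defect in an operative eligibility rule. Read literally, Exclusion 26 admits a patient who stopped a prohibited drug on day -1, with 1 to 6 days from stop to first dose. That a minimum of 7 days was intended is probable but unstated, and nothing in the documents justifies 7 days in particular.

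The number of patients affected cannot be estimated and could be zero. No bias, type I error or power consequence follows. The conclusion assumes counting in whole calendar days and first dosing inside the 5-day period of Section 5.3. The change is worth making because it is cheap and modestly safer, but the trial's conclusions would not depend on it.

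**What to change.** In the exception to Exclusion 26, replace 'within 7 days' by 'at least 7 days', with the sponsor to confirm that 7 days is the right minimum. No sentence preserving the longer limits elsewhere is needed: a patient must meet every inclusion and no exclusion, so an exception inside No. 26 cannot relax any other criterion.

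The cost is one phrase in an amendment. No new data are required, because medication use is already reviewed at Screening (Table 1) and stop dates are recorded (Section 5.13).

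A patient who stopped on day -1 would wait up to 7 − 1 = 6 more days. A screening item already *a* days old on the planned randomization date falls outside its window if *a* + 6 exceeds that window:

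- 14-day tests: *a* > 8 days.
- 28-day imaging: *a* > 22 days.
- 60-day echocardiogram or MUGA: *a* > 54 days.
- 12-week (84-day) resection limit: *a* > 78 days.

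The first three can be repeated, and Section 5.2.1 permits retesting within a Screening period. The last would cost the patient eligibility, but it should be rare.
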